Appendix A graphically depicts the timeline and associated measures

The Candidacy Evaluation and Preoperative Evaluation can either occur during the same visit or two different visits.

- 1. **Candidacy Evaluation.** This interval may overlap with the Preoperative Evaluation interval.
 - a. Audiologic Evaluation
 - i. Unaided air- and bone-conduction thresholds in both ears
 - a. Air-conduction assessed with inserts
 - ii. Unaided word recognition in both ears
 - a. Measured with recorded CNC words (50-word list)
 - b. Masking provided when appropriate
 - iii. Tympanometry in both ears
 - iv. Aided word recognition in the affected ear
 - a. Measured with recorded CNC words (50-word list)
 - b. Masking applied to the contralateral ear
 - v. Completion of the Tinnitus Handicap Inventory
 - vi. Determine if potential subject meets candidacy criteria
 - b. Medical Evaluation
 - i. Determine if potential subject is healthy enough to undergo cochlear implantation
 - ii. Associated imaging studies
 - a. This is standard of care for these patient populations
 - b. May also be completed at Preoperative Evaluation
 - iii. Discussion of alternative treatment options
 - iv. Determine if potential subject meets candidacy criteria
 - c. Informed Consent
 - i. Review and discussion of consent form
 - ii. Provide time for subject to review consent form and ask questions
 - iii. Provide subject with a signed copy of the completed consent form

2. **Preoperative Evaluation**. This interval may overlap with the Candidacy Evaluation interval.

The Preoperative Evaluation will be completed within 6 months of the surgery date.

- a. Audiologic Evaluation
 - i. Obtain a case history, including but not limited to:
 - a. Onset of hearing loss
 - b. Progression to moderate-to-profound sensorineural hearing loss
 - c. Suspected etiology of hearing loss
 - ii. Unaided air- and bone-conduction thresholds in both ears
 - a. Air-conduction assessed with insert phones
- iii. Unaided word recognition with CNC words in both ears
 - a. Measured with recorded CNC words (50-word list)
 - b. Masking provided when appropriate
- iv. Tympanometry in both ears
- v. Subjects will complete the test battery detailed in section VII.D.
 - a. Two listening conditions:
 - i. unaided
 - ii. bone-conduction test device or BAHA
 - a. The bone-conduction test device will be the Cochlear BAHA Intenso on a headband
 - b. If the subject has a BAHA (Cochlear Connect or Attract system) then her or she may use the external processor associated with that system.
 - b. Subjects who listen with a hearing aid in the contralateral ear may utilize this technology during this listening condition
 - i. Hearing aid output will be measured using the NAL-NL1 targets
- vi. Counseling on cochlear implant external technology, realistic expectations, study test battery, and postoperative timeline
- b. Medical Evaluation
 - i. Subjects will undergo a medical assessment and review of medical history
 - ii. Associated imaging studies
 - a. This is standard of care for these patient populations
 - b. May have been completed at Candidacy Evaluation
- iii. Counseling on cochlear implantation surgical procedure and postoperative considerations, including MRI limitations due to internal magnet
 - a. MED-EL Concert device approved for 0.2 or 1.5 Tesla

3. Surgery: Cochlear Implantation

Risk factors associated with cochlear implantation are listed in Section XI "Risk Analysis."

All surgical procedures will take place at the UNC Memorial Hospital or UNC Ambulatory Care Center (ACC) operating rooms. All procedures will be completed by board-certified otologists.

4. Postoperative Evaluations

- a. Initial Follow-Up (approximately 1-2 weeks postoperatively)
 - i. Medical Evaluation
 - a. This is standard of care
 - b. Subject will be seen by the physician
 - ii. Audiologic Evaluation
 - a. Unaided thresholds
 - i. Air-conduction assessed with an insert phone in the contralateral ear
 - ii. Bone-conduction thresholds assessed in the surgical ear
- b. Initial Activation of External Speech Processor (approximately 2-4 weeks postoperatively)
 - i. Unaided air and bone conduction thresholds
 - a. Air-conduction assessed with insert phones
 - ii. Unaided word recognition with CNC words in both ears
 - a. Measured with recorded CNC words (50-word list)
 - b. Masking provided when appropriate
- iii. Initial activation of external speech processor
 - a. Subjects will be fit with the commercially available MED-EL Opus 2 external speech processor (MED-EL Corporation, Innsbruck, Austria), and/or alternative external speech processor. Speech perception and localization measures at follow-up intervals will be conducted with the subject listening with the Opus 2 external speech processor for the aided conditions.
 - b. Mapping will be completed by board-certified audiologists. Mapping procedures will be similar to conventional cochlear implant recipients.
- iv. Counseling on the external device and use

c. One-Month Post-Initial Activation

- i. Completion of test battery listed in VII.D.
- ii. Speech perception assessed with the cochlear implant on and contralateral ear masked
 - a. CNC words
- iii. Mapping of the external speech processor
- d. Three-Months Post-Initial Activation
 - i. Completion of test battery listed in VII.D.
 - ii. Speech perception assessed with the cochlear implant on and contralateral ear masked
 - a. CNC words

- iii. Mapping of the external speech processor
- e. Six-Months Post-Initial Activation
 - i. Completion of test battery listed in VII.D.
 - ii. Speech perception assessed with the cochlear implant on and contralateral ear masked
 - a. CNC words
- iii. Mapping of the external speech processor
- f. Nine-Months Post-Initial Activation
 - i. Completion of test battery listed in VII.D.
 - ii. Speech perception with the cochlear implant on and contralateral ear masked a. CNC words
- iii. Mapping of the external speech processor
- g. Twelve-Months Post-Initial Activation (study endpoint)
 - i. Completion of test battery listed in VII.D.
 - a. Additional listening condition: bone-conduction test device or BAHA
 - ii. Speech perception with the cochlear implant on and the contralateral ear masked
 - a. CNC words
- iii. Mapping of the external speech processor
- D. Test Battery

The following test battery will be completed at each assessment interval (preoperative, and 1, 3, 6, 9 and 12 months postoperatively). All assessment and mapping will be conducted at the Carolina Crossing research lab by a board-certified audiologist.

- 1. Unaided Diagnostic Assessment
 - a. Air-conduction thresholds in both ears
 - i. Air-conduction assessed with insert phones
 - ii. Assess bone-conduction thresholds if there is a PTA shift of >15 dB as compared to the previous interval
- 2. Tympanometry for each ear
- 3. Sound Field Measures

The Carolina Crossing research lab features a 180° arc with 11 speakers spaced 18° apart. This arc will be utilized during the speech perception and localization measures.

Postoperative aided sound field assessment will be completed with the subject listening with the Opus 2 speech processor.

Subjects who utilize a hearing aid in the contralateral ear may continue to use this technology during the sound field test conditions where the contralateral ear remains open. Hearing aid output will be measured using NAL-NL1 targets.

- a. Aided thresholds with the external speech processor on will be measured using pulsed, warble tones
 - i. Frequencies assessed: 250-8000 Hz, including all inter-octaves
 - ii. Masking presented to the contralateral ear
- b. Speech Perception Measures

Recorded materials will be presented at 60 dB SPL.

- i. Speech Perception in Quiet
 - a. Listening condition
 - i. Speech 0° azimuth
 - b. Speech perception materials
 - i. CNC words
 - ii. AzBio sentences
- ii. Speech Perception in Noise
 - a. Listening conditions
 - i. Speech and noise 0° azimuth
 - ii. Speech 0° azimuth and noise to implanted side
 - iii. Speech 0° azimuth and noise to contralateral ear
 - b. Speech perception materials
 - i. AzBio sentences
 - a. If >50% at SNR+10, then SNR+5
 - b. If >50% at SNR+5, then SNR+0
 - ii. BKB-SIN sentences with adaptive SNR
- iii. Listening Conditions
 - a. Cochlear implant speech processor off
 - i. Contralateral ear only
 - b. Cochlear implant speech processor on
 - i. Cochlear implant + contralateral ear
- c. Localization
 - i. The stimulus is a 200-ms speech-shaped noise, presented at 70-dB SPL from one of the 11 speakers (evenly spaced -180 to 180 degrees), selected at random
 - ii. The intensity level for each stimulus presentation will be randomly varied (10 dB around 70 dB SPL)
 - iii. The listener will be facing the center speaker during stimulus presentation. The task is to identify the source of the noise. No feedback is provided.
 - iv. Listening Conditions

- a. Cochlear implant speech processor off
 - i. Contralateral ear only
- b. Cochlear implant speech processor on
 - i. Cochlear implant + contralateral ear
- 4. Subjective questionnaires
 - a. Speech, Spatial and Qualities of Hearing Scale (SSQ), Gatehouse & Noble (2004)
 - b. Abbreviated Profile of Hearing Aid Benefit (APHAB), Cox & Alexander (1995)
 - c. Tinnitus Handicap Inventory, Newman, Jacobson & Spitzer (1996)
- E. Aural Rehabilitation
 - 1. Subjects will participate in two aural rehabilitation sessions with a board-certified speech-language pathologist. One session will be after the initial activation of the external speech processor. This will occur either on the same day as the initial activation or within the first 2 weeks of listening experience. The second session will be scheduled in conjunction with the 1-month post-initial activation interval.

VIII. Proposed Claims

- A. Demonstrate the effectiveness of cochlear implantation in SSD subjects
 - 1. Demonstrate an improvement in speech perception abilities, localization, and/or subjective benefit in an aided (cochlear implant on) versus an unaided (cochlear implant off) condition
- B. Cochlear implantation provides similar or superior speech perception, localization, and/or quality of life as compared to that found with bone-conduction devices
 - 1. Comparison with control group performance
 - 2. Comparison within subject when listening with bone-conduction test device

IX. Statistical Analysis

- A. Descriptive summaries will be provided for the following: subject demographics, and frequency of major and minor complications/adverse events.
- B. A single-subject design will be utilized, where each subject serves as his or her own control, for analysis of objective and subjective results. A single-subject design was chosen in order to accommodate the heterogeneity that is well known to characterize auditory prosthesis research. Repeated-measures ANOVA will be calculated with a p-value of ≤ 0.05 for statistical significance. Statistical analysis will be conducted with SPSS software.
 - 1. Comparison of aided speech perception performance on word and sentence materials in the post-initial activation intervals to evaluate trends over time

- a. Comparison of the difference between the aided and unaided conditions at each follow-up interval
- 2. Comparison of localization abilities in the post-initial activation intervals
 - a. Comparison of the difference between the aided and unaided conditions for each follow-up interval
 - b. Compute the overall rms error, random error, constant error, and adjusted constant error, as described by Grantham et al (2007)
- 3. Comparison of subjective report scores in the post-initial activation intervals
- C. The incidence of interference between ears will be assessed by comparing the speech perception performance in the 0° azimuth conditions for the contralateral ear only versus cochlear implant + contralateral ear conditions for each subject, as well as the individual's subjective report.

A sample size for the cochlear implant recipient cohort of 20 subjects was selected due to known variability in conventional cochlear implant recipient outcomes and to allow for possible dropouts (approximately 20%). A comparable study, Hansen, Gantz & Dunn (2013) evaluated 29 cochlear implant subjects with SSD, which included etiologies of sudden sensorineural hearing loss, Meniere's disease, and vestibular schwannoma. Authors reported a high degree of variability in their sample. This project will not enroll all of the etiologies included in the Hansen, Gantz & Dunn (2013) analysis (such as, Meniere's Disease with intractable vertigo or history of vestibular schwannoma), therefore a smaller sample size was selected. The inclusion/exclusion criteria associated with this study, as compared to the heterogeneity of the Hansen, Gantz, & Dunn (2013) subject sample, will allow for more generalized comments about subjective and objective outcomes of cochlear implantation in cases of SSD.

If needed, statistical consultation will be sought from the North Carolina Translational and Clinical Sciences Institute (TraCS) or UNC Odum Institute.

X. Endpoints

- A. Safety endpoint
 - 1. The primary safety endpoint is the evaluation of Adverse Events. All Adverse Events will be reported to the UNC IRB. If the UNC IRB or study investigators deem an Adverse Event unacceptable, then this would result in termination of the study.
- B. Primary effectiveness endpoint
 - 1. The primary effectiveness endpoint is the comparison of speech perception, localization abilities and/or subjective report when the cochlear implant is on versus off.
- XI. Risk Analysis

A. Potential risks

The following are risks associated with the MED-EL Concert implant, which is also included in the device description:

- 1. Loss of residual hearing
- 2. Increased vertigo
- 3. Delay of healing of the scar
- 4. Impairment of the sense of taste
- 5. Potential for swallowing difficulties
- 6. Numbness
- 7. Increased tinnitus
- 8. Stimulation of the facial nerve
- 9. Temporary pain and uncomfortable sounds during stimulation

The following are potential risks the subject may experience related to the study procedure:

- 1. Surgical
 - a. Facial nerve injury
 - i. Facial nerve monitoring is conducted during the surgical procedure
 - b. Infection
 - i. All subjects will be counseled regarding bacterial meningitis and recommended vaccinations
 - c. Bleeding
 - d. Cerebrospinal fluid (CSF) leak
 - e. Pain
 - f. Scarring

2. Postoperative

- a. Swelling around the incision and/or coil site
- b. Pain

i.

- c. Reduced or loss of pinna sensitivity on the surgical side
 - Typically resolves 1-2 months postoperatively
- d. The cochlear implant may not provide any auditory stimulation
- e. The cochlear implant may provide auditory stimulation, but with a sound quality too poor to aid in the perception of speech
- f. The cochlear implant may provide auditory stimulation, but with a sound quality too poor to aid in localization
- g. Pain associated with the coil and/or placement of the external speech processor on the subject's ear
- h. Movement of the internal receiver
- i. Discomfort from electric stimulation
- j. Facial nerve stimulation
- k. Headache

- 1. Dizziness
- m. Altered taste (i.e. reports of metallic tastes on the same side of the tongue as the surgical ear)
- n. Fatigue during follow-up assessment (completion of the test battery and/or mapping)
- o. The internal device may fail, requiring revision cochlear implantation
- p. The sound from the cochlear implant may interfere with the better hearing ear.
- B. Risk Mitigation
 - 1. Current hearing device options, including CROS hearing aids and bone-conduction devices, would still be available to the subject in the future if the subject does not benefit from the cochlear implant or elects to no longer use the cochlear implant.
 - a. The test battery includes a listening condition to assess the monaural performance of the contralateral ear. Interference of the cochlear implant on the performance of the contralateral ear can be evaluated by comparing the contralateral ear only condition to the cochlear implant + contralateral ear conditions when tested at 0° azimuth, as well as, review the subjective benefit via the subjective questionnaires. If interference is found to impact speech perception and subjective benefit, the subject may elect to discontinue use of the cochlear implant and would still have access to currently approved technologies for SSD.
 - 2. Magnet strength will be assessed at each interval to ensure comfort at the coil site.
 - 3. Reports of pain from the external speech processor placement will be addressed by different wearing options (i.e. moleskin between the external speech processor and the subject's ear, or different battery-wearing options to lighten weight on the pinna).
 - 4. Mapping will be conducted at each post-initial activation interval to improve audibility and comfort of the sound quality from electric stimulation.
 - 5. The MED-EL cochlear implant has MRI limitations*. Subjects may have CT scans or x-ray imaging postoperatively when warranted.
 - a. *The MED-EL CONCERT cochlear implant is approved for MRI of 0.2 or 1.5 Tesla
 - 6. An otologist will conduct medical follow-up evaluations at the 6 and 12-month intervals, which is standard of care for cochlear implant recipients.
 - 7. Age appropriate vaccinations per the CDC recommendations will be completed by each subject prior to implantation. Subjects will be counseled regarding meningitis vaccinations and directed where to obtain them by their implanting physician.

XII. Potential Benefits

- A. Improvement in speech perception abilities in noise with the cochlear implant due to utilization of auditory cues from both ears.
- B. Improvement in localization abilities with the cochlear implant due to utilization of auditory cues from both ears.
- C. Improvement in subjective benefit with the cochlear implant as compared to preoperative performance.

The potential benefits of cochlear implantation in cases of SSD are suspected to outweigh the risks listed in Section XI.A. The study sample will include subjects with previous history with current hearing technology options for SSD, who are dissatisfied with this technology and/or have discontinued use of the technology. This sample is similar to those in previously published reports who have benefited from cochlear implantation.

This study also includes a comparison to a currently approved technology option for SSD, boneconduction technology. This comparison will be used to assess outcomes between technologies, but also to determine whether individual subjects experience differences in performance between the two technologies. The risks associated with cochlear implantation in this population are also reduced considering subjects may continue to use currently approved technologies for SSD if they do not obtain subjective and objective improvements from cochlear implantation.

XIII. Adverse Events

- A. Anticipated versus Unanticipated Events
 - 1. Anticipated Events: those events described as potential risks (section XI.A.) of the protocol
 - 2. Unanticipated Events: events not reported as potential risks (section XI.A.)
 - a. Unanticipated serious adverse events are defined as any serious adverse event related to the health or safety or any life-threatening problem or death caused by, or associated with, a device, if that event, problem, or death that was not previously defined in nature, severity, or degree of incidence in the literature or investigational plan. It can also include any other unanticipated serious problem associated with a device that relates to the rights, safety or welfare of subjects.
 - 3. Serious Adverse Event: Serious injury means an injury or illness that: 1) is lifethreatening, 2) results in permanent impairment of a body function or permanent damage to a body structure, or 2) necessitates medical or surgical intervention to preclude permanent impairment to a body function or permanent damage to a body structure.
 - a. Permanent means an irreversible impairment or damage to a body structure or function, excluding trivial impairment or damage.
 - b. Revision cochlear implantation will be considered a serious anticipated adverse event.
- B. Reporting adverse events
 - 1. All adverse events will be reviewed by the PI during the preparation of the annual reports to the FDA and UNC IRB. Combined adverse events will be listed in an excel spreadsheet. Frequent adverse events will be discussed with co-investigators.
 - 2. Anticipated events will be reported to the FDA in the annual report

3. Unanticipated events will be reported to the FDA and UNC IRB within 10 days of the investigator becoming aware of the event, as required by 21CFR 812.150.

XIV. Monitoring

- A. Subjects will be monitored on a case-by-case basis for ongoing or unanticipated medical complications. Adverse events will be tracked on a case-by-case basis and recorded in study binders at the time of occurrence and followed up at resolution. Any adverse event will be reported to the UNC IRB. Should there be concern for the safety of subjects because of their participation in the study by the investigators or the UNC IRB, the study would be halted at least temporarily and a detailed discussion with the investigators and UNC IRB would be undertaken to evaluate the viability of the study.
- B. Subjects can withdraw from the study at any time and for any reason by notifying the Primary Investigator. If the investigator identifies the need to withdraw a subject from the study for any reason, this will be discussed in person during a scheduled evaluation. Subjects may also be withdrawn if residual hearing changes in the contralateral (better hearing ear) to a moderate hearing loss of worse. In either scenario, the subject will continue to receive care irrespective of their participation in the study.

C. Investigative Team

- 1. The Principal Investigator will review completed Consent Forms and Case Report Forms, including determining candidacy.
- 2. The Principal Investigator will ensure that study site Standard Operating Procedures are followed by the study team.
- 3. Responsibilities for all study team members will be recorded in a Study Delegation Log. Not all team members will be responsible for all activities.
- 4. Communications between the Principal Investigator and study team will be maintained in the regulatory binder.
- 5. Source data will be maintained with completed Case Report Forms (such as, speech perception score sheets) when available.

XV. Confidentiality

- A. Subjects will be assigned a specific, anonymous subject number that will be associated with his or her data. Database entry will be by subject number only. All personal identifiers will be kept in a separate, secure data file that will be password protected and not associated with the study data. Only investigators will have access to the subject numbers.
- B. Subject specific binders will be maintained in a locked cabinet in the Carolina Crossing research lab. Individual data collection sheets will be coded with the subject number and placed in the subject specific binder at each interval. For analysis, the data will not included identifiable information.

- C. Data will not be shared outside the investigative team except during reporting of anonymous results.
- D. After the closure of the study, subject data will be retained for seven years. At that time, paper data will be shredded and destroyed in a HIPAA compliant manner. Electronic data will be destroyed following UNC policy.
- E. A description of the clinical trial will be available on http://ClinicalTrials.gov. This web site will not include information that can identify research subjects.

XVI. References

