Root-Mean-Square (rms) Error: The difference between the location on the azimuth of the sound source and the subject's response on each trial for the localization task

Single-Sided Deafness (SSD): Severe-to-profound sensorineural hearing loss with limited speech perception in one ear and a normal to mild hearing in the contralateral ear

V. Investigational Device

A. Subjects will be implanted with the commercially available MED-EL CONCERT cochlear implant with the standard electrode array (MED-EL Corporation, Innsbruck, Austria). The device consists of a stimulator, a coil with a magnet within its center, a reference electrode, an EAP reference electrode and an active electrode permanently attached to the stimulator. The electrode is made of medical grade silicone, platinum (electrode contacts) and platinum/iridium (90/10) wires and nitinol.

The purpose of the device is perception of environmental sound and potential for improvement in communication abilities.

For the adult population, the MED-EL CONCERT cochlear implant is indicated for those 18 years of age or older, who have bilateral sensorineural hearing impairment and obtain limited benefit from appropriately fitted binaural hearing aids.

The standard electrode array is 31.5 mm long, with 12 pairs of contacts spaced over 26.4 mm with 2.4 mm spacing between each contact pair. The electrode's length allows insertion into the scala tympani and stimulation of the cochlear canal to the fullest extent possible. The array features a marker ring 31.5 mm from the apex that is used to seal the cochleostomy and to indicate maximum electrode insertion. The diameter of the array increases to 1.3 mm at the proximal thicker part of array just before the marker ring.

Subjects will be fit with the Opus 2 speech processor. The Opus 2 speech processor is an external component of the MAESTRO Cochlear Implant System and is indicated for use on patients who have been implanted with a MED-EL cochlear implant. The Opus 2

audio processor consists of the control unit with the earhook attached, the battery pack frame and cover, the connecting piece, the coil and the coil cable. The audio processor uses batteries that provide sufficient power for both the external and the implanted electronics.

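### The localization task text places the 11 speakers at -180 to 180 degrees, contradicting the stated 180° arc at 18° spacing (-90 to 90); linear scoring on the task-text angles would double the reported errors in degrees.

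*Combined protocol and SAP*

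**What the plan says.** Section VII.D.3 (Sound Field Measures) describes the apparatus: "The Carolina Crossing research lab features a 180° arc with 11 speakers spaced 18° apart". It continues: "This arc will be utilized during the speech perception and localization measures".

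Section VII.D.3.c.i (Localization) then says the stimulus is "presented at 70-dB SPL from one of the 11 speakers (evenly spaced -180 to 180 degrees), selected at random". Two items later, the same list fixes the listener's orientation: "The listener will be facing the center speaker during stimulus presentation".

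Section IV (Definitions) gives rms error as "The difference between the location on the azimuth of the sound source and the subject's response on each trial for the localization task". Section IX.B.2.b lists the planned indices: "Compute the overall rms error, random error, constant error, and adjusted constant error". Section IX.B.2.a compares aided with unaided localization at each follow-up, and Section IX.B names repeated-measures ANOVA as the method. Section X.B makes localization, implant on versus off, one of three components of the primary effectiveness endpoint.

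Neither the definitions nor the analysis section says which speaker coordinates are used for scoring, or whether angular differences are taken linearly or wrapped to within ±180°.

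**The concern.** The two descriptions concern the same 11 speakers and give different geometries. The task text is the only place that assigns a numeric range of source angles, so a person building the scoring sheet from it could code the speakers on the wrong scale. All four planned indices are computed from coded azimuths in degrees and would carry the error directly.

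What is at stake is the localization error reported in degrees, in a primary effectiveness domain, and any reading of those degrees against published values or a chance level. The background text makes such a reading likely, since it says that localization with existing devices has been found to be at chance.

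**Working it through.** **Inputs.** 11 speakers, a 180° arc and 18° spacing (Section VII.D.3); 11 evenly spaced speakers from -180 to 180 (Section VII.D.3.c.i); listener facing the center speaker (Section VII.D.3.c.iii); error definitions (Section IV).

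**1. Reproduce the apparatus figure.** Span = (11 - 1) × 18° = 180°. With the listener facing the sixth speaker, the positions are -90, -72, -54, -36, -18, 0, 18, 36, 54, 72 and 90. The apparatus text is consistent in itself.

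**2. Test the task text.** Spacing = 360° / (11 - 1) = 36°, twice the stated value. The positions are -180, -144, -108, -72, -36, 0, 36, 72, 108, 144 and 180. The two end positions are one physical point, so there are only 10 distinct positions, and six of the 11 coded angles (±108, ±144, ±180) lie behind the listener. That is not a 180° arc.

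**3. Effect on the indices under linear coding.** Each task-text angle is twice the arc angle, so every signed difference d becomes 2d.

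- Rms error: sqrt(mean((2d)²)) = 2 × sqrt(mean(d²)).
- Random error: a standard deviation of doubled responses is doubled.
- Constant error: the rms of doubled mean deviations is doubled.
- Adjusted constant error: the bias removed is also doubled, so the result is doubled.

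Illustration with responses spread uniformly over the 11 positions. In speaker steps from the center, the mean square is 110/11 = 10.

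- Arc coding: sqrt(2 × 18² × 10) = sqrt(6480) = 80.5°.
- Task-text coding: sqrt(2 × 36² × 10) = sqrt(25920) = 161.0°. The ratio is 2.

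**4. Effect if differences were wrapped to ±180°.** For the same uniform responses, the wrapped differences have a mean square of 1020/121 in units of 36° steps. The rms is 36 × sqrt(1020/121) = 104.5°, or 104.5/80.5 = 1.30 times the arc value. In simulated poor localizers the ratios across the four indices ran from about 0.6 to 3.1. In a simulated good localizer all four were still 2.0. Exact doubling therefore depends on linear differences.

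**5. Effect on the planned test.** If every score is multiplied by 2, the effect and error mean squares in the ANOVA are both multiplied by 4, and their ratio is unchanged. A simulated paired comparison with 20 subjects gave t = -6.79 on either scale.

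**The case against.** The strongest reply is that the apparatus text already settles the matter. It says the arc is the one used for localization, the listener faces the center, and the definitions measure error from where the source is. Read together these give -90 to 90, and the task text looks like a drafting slip. That stands as to which geometry is intended. It does not make the operative line correct, because that line is the one giving the source angles.

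It is also fair to say that no planned inference is harmed by a common scale factor. Section X.B compares on with off within subject. The bone-conduction control group completes the same battery, all assessment is at one laboratory, and a shared factor would cancel there too. Section IX plans no test against chance and no numerical comparison with published degrees. All of this stands and limits the point to the reported degrees.

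A reader might infer that every localization error in the trial is doubled. The documents do not support that. No section says scoring uses the task-text angles, and exact doubling also needs linear, unwrapped differences.

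A reader might also reason that a true 40° rms reported as 80° would look like chance performance. That sets a value on the doubled scale against chance on the undoubled scale; on the doubled scale, uniform guessing gives 161.0°. Likewise, counting confusion of the end speakers as a 360° error between coincident points mixes the two layouts: on the real arc those speakers are 180° apart.

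**Conclusion.** The contradiction is certain: the range in Section VII.D.3.c.i is wrong if Section VII.D.3 is right, and only -90 to 90 fits 11 speakers 18° apart with the listener facing the center.

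The consequence is conditional. If sources and responses were coded linearly with the task-text angles, all four indices would be reported at exactly twice their true size in degrees. Linear coding is the natural reading of the Section IV definitions, which mention no wrapping, but it is not stated. With wrapping, the distortion would not be a constant factor, and invariance of the on-versus-off test could no longer be assumed.

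Under linear coding used consistently, the on-versus-off test is unaffected. Nothing shows that any score has been miscoded, and no sample size, power or significance level depends on this. It remains worth correcting because the wrong figure sits in the operative procedure for a primary effectiveness domain.

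**What to change.** In Section VII.D.3.c.i, replace the range with -90 to 90 degrees, evenly spaced at 18°, to match Section VII.D.3. Add one sentence stating that source and response azimuths are coded on this scale for all groups, conditions and visits. Check the scoring sheet against it.

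No chance reference value needs to be prescribed. The 80.5° figure assumes uniform guessing, which the plan does not state. On the same arc, always answering the center speaker gives sqrt(18² × 10) = sqrt(3240) = 56.9°, and always answering one end speaker gives sqrt(90² + 3240) = sqrt(11340) = 106.5°.

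The cost is a short text correction and a check of the scoring sheet. No new data are needed.
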